After the treatment has been washed out on Day 7 the investigator will demonstrate application of the blinded test preparation (either Octanediol 1% Solution or placebo) to the parent/care giver. After this demonstration the investigator will provide a sufficient quantity of test preparation for the parent/care giver to use over the following period.

Participants will be assessed weekly by a member of the MEC study team who is unaware of the treatment that was applied. One day before each visit is due; the parent/care giver will be sent an SMS (text) message to remind them of the appointment. If the parent/care giver does not have a mobile telephone, a landline telephone call will be made as an alternative.

If no lice are found at the regular weekly assessments, the investigator will replenish the supply of investigative product, and collect the used bottle(s) of investigative product during the routine visit.

It is possible that lice may be found at an assessment visit. However, due to the nature of the product and its mode of action this discovery does not necessarily confirm that an infestation has been established. Consequently, on the first discovery of a louse a note will be made in the CRF but no further action will be taken that day. At the next assessment visit if any lice are found, or if at any single visit ≥ 5 adult lice or any stage 1 or stage 2 nymphal lice are found, a sample will be collected and taped into the participant's CRF. The participant will then be treated using Hedrin Once liquid gel in a similar manner to the treatment on Days 0 and 7. After the second treatment the participant will continue in the same treatment arm until completion of the six week participation period for that treatment.

At the end of six weeks each participant will be treated again using Hedrin Once liquid gel to eliminate any lice present, or that have been missed by investigators during the combing assessments. Two applications of product will be made 7 days apart, with combing during the second application to ensure no lice are present. This will constitute a "wash-out" to ensure all participants start the second arm of the study louse free as at the beginning. Each Participant will then be crossed-over to the other treatment arm of the study, i.e. anyone who received Octanediol 1% Solution initially would receive placebo or anyone on placebo would receive Octanediol 1% Solution.

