3.1.2 Efficacy

The primary endpoint is the frequency of not contracting an infestation by head lice during the course of the study, indicated by no evidence of active head louse infestation.

The main secondary endpoint will be comparison of the frequency (number) of instances of reinfestation.

The other secondary endpoints are the safety and acceptability of the Octanediol 1% Solution preparation in regular use.

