3.3 Proposed Primary and Secondary Analyses

1. To confirm that Octanediol 1% Solution can prevent the development of a head louse infestation either by killing lice that climb onto the head or so limit their viability that an infestation does not develop.
2. To compare the efficacy of Octanediol 1% Solution with that of a placebo in the prevention of head louse infestation.
3. To compare Octanediol 1% solution with placebo in the time to first infestation.
4. To compare the number of times each participant is infested while treated with Octanediol 1% Solution compared with the number of times they are infested while treated with placebo

5. To evaluate Octanediol 1% Solution in terms of safety and acceptability.

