In order to partially address the problems outlined above it is planned to mostly recruit from contacts, obtained from previous clinical studies, who have expressed an interest to take part in a study of this type. This group is known to be more at risk. Therefore, based on past study data relating to when people have contracted lice after study treatments, there is a reasonable expectation of an infestation rate of between 3 and 5 instances of reinfestation per year for each person in that group, i.e. a risk of about 3.6-4 possible reinfestation events per week for the whole study population. This doesn't mean that they will get lice but rather that they could come into contact with someone who does have them and lice could therefore be passed to them.

An estimation of sample size was made using conventional "survival analysis" calculations and the table below is taken from http://www.stattools.net/SSizSurvival_Pgm.php.

The table of sample size for 2 survival ratios is applicable to the common situation where the probability of Type I error $\alpha = 0.05$ (95% confidence) and power = 0.8 (80% power). In conventional survival analysis terms it assumes that the sample size in each of the two arms is the same, which in this case is certainly correct because each individual participates in both treatment arms sequentially.

The rows and columns represent the anticipated proportions of participants remaining louse free in each of the two treatment arms, and each cell is the total sample size (both treatment arms together) for that row/column combination. The shading covers the anticipated range of outcomes. These estimations of size that are proposed for this study appear to be at around the lower bound of population size required for the 30-35% difference in outcome between treatments necessary to detect superiority (range 62-90 participants) using a cross-over model, thus fulfilling the preferred aim of minimising the number of participants in the study.

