For a randomise-by-individual approach, assuming a confidence level of 95% and a power of 80%, and anticipating the expected non-infestation rates to be 65% for Octanediol 1% Solution and 30% for the placebo, the required sample size is therefore estimated as 34 subjects per treatment. However, this study will operate a “hybrid” randomization in that only one person from each household will be randomized (index case) and all others in the house will be offered treatment when infestation arises but will continue to potentially act as a source of reinfestation. This approach reduces possible confounding issues of enrolling all members, in which some households will have all members on one intervention but others will have a mixture of active and placebo interventions. Therefore, for each participant on each arm of the cross-over the familial risk of reinfestation should be similar in this respect.

Sample size table for 2 hazard ratios in survival analysis

| | 0.05 | 0.10 | 0.15 | 0.20 | 0.25 | 0.30 | 0.35 | 0.40 | 0.45 | 0.50 | 0.55 | 0.60 | 0.65 | 0.70 | 0.75 |
|------|------|------|------|------|------|------|------|------|------|------|------|------|------|------|------|
| 0.10 | 496 | | | | | | | | | | | | | | |
| 0.15 | 173 | 963 | | | | | | | | | | | | | |
| 0.20 | 99 | 295 | 1414 | | | | | | | | | | | | |
| 0.25 | 69 | 155 | 406 | 1826 | | | | | | | | | | | |
| 0.30 | 53 | 100 | 203 | 504 | 2186 | | | | | | | | | | |
| 0.35 | 43 | 73 | 127 | 245 | 588 | 2486 | | | | | | | | | |
| 0.40 | 36 | 57 | 90 | 149 | 280 | 656 | 2723 | | | | | | | | |
| 0.45 | 32 | 47 | 68 | 103 | 167 | 307 | 708 | 2894 | | | | | | | |
| 0.50 | 28 | 39 | 54 | 77 | 114 | 181 | 326 | 743 | 2997 | | | | | | |
| 0.55 | 26 | 34 | 45 | 60 | 83 | 121 | 190 | 338 | 761 | 3032 | | | | | |
| 0.60 | 24 | 30 | 38 | 49 | 65 | 88 | 126 | 195 | 343 | 761 | 2999 | | | | |
| 0.65 | 22 | 27 | 33 | 41 | 52 | 67 | 90 | 128 | 195 | 339 | 744 | 2897 | | | |
| 0.70 | 21 | 25 | 30 | 36 | 43 | 54 | 69 | 91 | 127 | 192 | 328 | 711 | 2727 | | |
| 0.75 | 20 | 23 | 27 | 31 | 37 | 44 | 54 | 68 | 89 | 123 | 183 | 310 | 660 | 2490 | |
| 0.80 | 19 | 22 | 24 | 28 | 32 | 37 | 44 | 54 | 66 | 86 | 116 | 171 | 284 | 592 | 2186 |
| 0.85 | 18 | 20 | 23 | 25 | 28 | 32 | 37 | 43 | 52 | 63 | 80 | 107 | 154 | 250 | 508 |
| 0.90 | 18 | 19 | 21 | 23 | 26 | 28 | 32 | 36 | 42 | 49 | 59 | 73 | 95 | 133 | 209 |
| 0.95 | 17 | 19 | 20 | 21 | 23 | 25 | 28 | 31 | 34 | 39 | 45 | 53 | 64 | 81 | 108 |

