However, if no censoring occurs, it may be more appropriate, because the primary outcome measure is no evidence of active head louse infestation, that the primary analysis method could additionally use the McNemar's test on these binary outcome (evidence/no evidence of active head louse infection during the treatment period) data as a simple method to address point 1. of section 3.3, to answer the question as to whether the Octanediol 1% Solution is able to prevent establishment of a head louse infestation.

In addressing point 4. of section 3.3, which may potentially result in a ranked variable, from how many times each individual becomes infested over the course of each arm of the crossover, the Wilcoxon signed rank test will be used for the paired data derived from the time spent in each arm of the study by each participant.

Because this is a cross-over study there will be no conventional comparison of difference between groups in baseline characteristics. However, the two arms will be tested for comparability of some baseline characteristics, such as presence of infestation, and presence of infestation in other household members at the start of the study and at the commencement of the "wash-out" cross-over treatment. For these comparisons, and comparisons of safety, and acceptability data will be tested using Fisher's exact test for yes/no variables and the Wilcoxon signed rank test for paired data, or Mann-Whitney U test for unpaired, ranked variables.

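### Yes/no safety and acceptability data are assigned Fisher's exact test, although the cross-over makes between-product yes/no data paired; if responses within a person are positively correlated, power is lost

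*Protocol*

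**What the plan says.** The last paragraph of Protocol section 3.4 (Analytical Methods) names the tests for baseline comparability and for safety and acceptability. For the latter, "safety, and acceptability data will be tested using Fisher's exact test for yes/no variables"; the sentence then adds "the Wilcoxon signed rank test for paired data, or Mann-Whitney U test for unpaired, ranked variables". Yes/no variables therefore get one test, for independent groups. The paired and unpaired alternatives follow with the ranked variables.

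The design is within-person. Section 1.4 says "Each Participant will then be crossed-over to the other treatment arm of the study", section 2.3.3.4 repeats the procedure, and the sample size text in section 3.4 notes that "each individual participates in both treatment arms sequentially". Adverse events are to be entered in the case record form at the follow-up visits (section 2.3.3.3) and again under the cross-over and final assessment (section 2.3.3.4), so both periods are covered.

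For the binary efficacy outcome, the same part of section 3.4 says that "the primary analysis method could additionally use the McNemar's test on these binary outcome", which is a paired test.

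On the standing of these data, section 3.1.2 says "The other secondary endpoints are the safety and acceptability of the Octanediol 1% Solution preparation in regular use", and item 5 of section 3.3 reads "To evaluate Octanediol 1% Solution in terms of safety and acceptability".

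**The concern.** Fisher's exact test treats the records on the two products as coming from different people. Applied to 68 active and 68 placebo period records, it counts each participant twice and discards the link between the two records. Section 3.4 argues for the cross-over because each participant serves as his or her own control, and the plan uses that pairing for efficacy (McNemar's test, signed rank test) but not for yes/no safety and acceptability data.

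Positive correlation within a person is plausible: the same scalp is exposed, and the same child and carer report on both products. The variance of the difference between the two proportions is then smaller than Fisher's test assumes. The test becomes conservative, and a real difference, for example in scalp reactions, is easier to miss. For safety that is the unhelpful direction.

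**Working it through.** **1. The plan's own figure.** The protocol gives no number for the safety comparison. Its only sample size figure is 34 per treatment (68 in total), for 65% vs 30% free of infestation, alpha 0.05 and power 80% (section 3.4). Two-sided alpha is an assumption, and it reproduces the figure with the Freedman log-rank formula:

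- Hazard ratio = ln 0.65 / ln 0.30 = 0.358.
- Events = (1.960 + 0.842)² × [(1 + 0.358)/(1 − 0.358)]² = 35.09.
- Mean event proportion = (0.35 + 0.70)/2 = 0.525.
- Total = 35.09 / 0.525 = 66.8, hence 67 (the table cell in section 3.4), or 34 per treatment.

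This figure concerns efficacy and does not depend on the point made here.

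**2. Inputs for the safety comparison.** From the protocol: 68 participants, hence at most 68 complete pairs, and alpha 0.05 (taken as two-sided). Assumed, because the protocol gives none: the event rates p1 and p2 on the two products, and the within-person correlation phi.

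**3. Model.** For each pair:

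- event on both: p11 = p1·p2 + phi·√[p1(1 − p1)·p2(1 − p2)]
- first product only: p10 = p1 − p11
- second product only: p01 = p2 − p11
- neither: p00 = 1 − p11 − p10 − p01

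Example, 20% vs 5%, phi 0.3: p11 = 0.20 × 0.05 + 0.3 × √(0.16 × 0.0475) = 0.010 + 0.026 = 0.036, so p10 = 0.164, p01 = 0.014 and p00 = 0.786.

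All possible outcomes for 68 pairs were enumerated with their multinomial probabilities. Fisher's test was applied to the two margins as if they were independent groups of 68. Exact McNemar was applied to the discordant pairs (binomial with probability ½). Both were two-sided at 0.05.

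**4. Power.**

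| Assumed rates | phi | Fisher | Exact McNemar |
|---|---|---|---|
| 20% vs 5% | 0 | 70.5% | 69.7% |
| 20% vs 5% | 0.1 | 71.4% | 74.0% |
| 20% vs 5% | 0.2 | 72.4% | 79.1% |
| 20% vs 5% | 0.3 | 73.6% | 84.9% |
| 25% vs 10% | 0.3 | 57.8% | 71.6% |
| 50% vs 30% | 0.3 | 61.9% | 75.1% |
| 10% vs 5% | 0.3 | 7% | 13% |
| 8% vs 3% | 0.3 | 8% | 13% |
| 5% vs 1% | 0.3 | 5% | 6% |

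At 20% vs 5%, phi cannot exceed (0.05 − 0.01)/√(0.16 × 0.0475) = 0.46, so larger correlations are not possible there. With slightly negative correlation (phi −0.1) Fisher's test is the stronger of the two, 69.7% against 65.8%.

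**5. True size with no difference (20% on each product).** Fisher against exact McNemar: 3.1% vs 3.0% at phi 0, 1.0% vs 2.8% at phi 0.3, and 0.3% vs 2.3% at phi 0.5. Neither test exceeds the nominal 5%.

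**The case against.** **The sentence is loosely drafted.** It covers baseline, safety and acceptability comparisons at once, and the signed rank test might be meant for paired data in general. The authors plainly know McNemar's test, so this may be a slip that a statistical analysis plan would settle. That softens the point but does not remove it: as written, yes/no variables are expressly given Fisher's test, and no other section corrects it.

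**Fisher's test suits part of what the sentence covers.** It is appropriate for comparing the two sequence groups, for instance on infestation at entry. This stands, and the point is confined to comparisons between products.

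**The pairing is not shown for acceptability.** A reader might infer that every participant gives one acceptability answer per product. The protocol does not say how or when acceptability is collected, and the Completion/Withdrawal Form is filled in once, at the end. For acceptability the point is therefore conditional.

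**The consequence can be overstated.** A reader might conclude that the plan will hide safety differences and so fail the second aim in section 1.3. The documents do not support that. The second aim is to confirm the product's safety and acceptability profile, and item 5 of section 3.3 speaks of evaluating, where items 2 to 4 speak of comparing; only the sentence in section 3.4 turns safety into a between-product comparison. The loss of power also depends on a correlation that the protocol does not give. It nearly vanishes at phi 0 to 0.1, and for rare events neither test has useful power.

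**McNemar's test has costs.** It leaves out participants with only one period, while the intention-to-treat population in section 3.2 keeps premature terminations, including those due to adverse events. It also makes no adjustment for period. Both limits stand and are taken up in the change proposed.

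**Conclusion.** The point holds as a correction to one sentence about secondary endpoints. The protocol names an independent-groups test for data that are paired by design: clearly so for adverse events, and for acceptability if it is recorded for each product.

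The error is conservative. It does not inflate false positives, but it can make a real safety difference easier to miss. In the settings tried with commoner events (20% vs 5%, 25% vs 10%, 50% vs 30%), the loss at phi 0.3 is about 11 to 14 percentage points of power. It is under 3 points at phi 0.1 (20% vs 5%) and practically nil at phi 0. These figures rest on assumed rates and correlations, 68 complete pairs and a two-sided 0.05 level. The primary analysis and the sample size of 34 per treatment are not affected.

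**What to change.** In the last paragraph of section 3.4:

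- For yes/no safety and acceptability data compared between products, use exact McNemar's test with a paired risk difference and 95% confidence interval, in participants with data from both periods.
- Report event counts by product for everyone treated, including those who left before the cross-over, so that withdrawals for adverse events stay visible.
- Keep Fisher's exact test and the Mann-Whitney test for comparisons between the two sequence groups.

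This changes one sentence and adds a reporting line; adverse events need no new data. For acceptability, the paired test presupposes an answer for each product. The small downside is that McNemar's test sets aside single-period participants and does not adjust for period.

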3.5 Final Study Report

A clinical report, integrating the study design and the results will be prepared for the study and agreed by the Chief Investigator and the Study Managers. The Chief

Investigator, the Clinical Research Manager, and representatives of Thornton & Ross Ltd will sign a copy of the final study report.

4 ADMINISTRATIVE PROCEDURES

4.1 Regulatory Documentation

Any required legislative procedures will be undertaken before the commencement of the study. The study will not proceed without granted written approval.

This study will be conducted according to the recommendations of the European (CPMP) Guidelines on Good Clinical Practice for Trials on Medicinal Products and with the European Standard, and the EU Directive on Good Clinical Practice (2001/20/EU).

4.2 Ethics Committee Approval

The Chief Investigator will be required to obtain the written approval of the relevant Research Ethics Committee before commencing the study. In accordance with Good Clinical Research Practice, a copy of this approval together with the constitution of the ethics committee will be forwarded to Thornton & Ross Ltd before the release of trial supplies from Thornton & Ross Ltd.

4.3 Informed Consent

This study will be conducted in accordance with the principles laid down in the Declaration of the World Medical Assembly of Helsinki, and subsequent revisions (see Appendix 1).

Each participant or parent/guardian (where the participant is not legally competent) will be requested to provide written informed consent after receiving written information and a verbal explanation of what the study involves. A copy of the Consent Form will be returned to the participant and/or parent/guardian.

The Investigator will retain the original of the Consent Form, but will also complete a Declaration of Receipt of Consent Form to confirm that written informed consent was obtained. The Investigator shall arrange for the retention of participant identification codes for at least 25 years after the completion or discontinuation of the study.

4.4 Insurance Policy

Thornton & Ross Ltd confirms that this specific clinical study is protected by insurance cover which provides an indemnity to the Investigators and their co-workers, subject to the Policy terms, conditions and limitations and provided always that the study is conducted and the data as reported agree to the standards fixed by the protocol. Indemnity, in the event of negligent acts by investigators in the field, must be covered by the professional liability insurance of the appropriate institution employing them.

4.5 Compensation

Thornton & Ross Ltd maintains in force a "no fault" compensation insurance indemnity in accordance with the current version of the ABPI Guidelines on Clinical Trials: "Compensation for Medicine Induced Injury". In the event that the compensation on a "no fault basis" is unacceptable to the claimant, the Policy will, subject to its terms, conditions and limitations, respond to an action for legal liability arising out of this clinical study.

4.6 Investigator's Responsibilities

Good Clinical Practice

It is the responsibility of the Investigators to ensure that this study is carried out in accordance with this protocol in respect of ethical, legal and technical aspects and conforming to the European (CPMP) Guidelines on Good Clinical Practice for Trials on Medicinal Products. In this context, the Investigator shall arrange for the retention of participant identification codes for at least 25 years after completion or discontinuation of the study. Thornton & Ross Ltd will render all support necessary to assist the Investigator in discharging this responsibility.

Replacement of Principal Investigator

In the event of a Chief/Principal Investigator being unable to continue the study, another responsible person may be designated Investigator and documentation testifying to this will be submitted to the study monitor and the Research Ethics Committee within 10 days. The new Investigator must be appropriately qualified and be approved by Thornton & Ross Ltd and the Research Ethics Committee before the study can be continued.

Study Report

The Chief Investigator will submit a summary study report within approximately 2 months of completion of the study. This report will include:

1. Details of the investigative procedures involved.
2. The numbers of participants entered, completed, and withdrawn from the study.
3. Deviations from the study protocol on a general basis and for individual participants, with explanations.
4. Explanations for each participant withdrawn from the study.
5. Methodology and normal ranges for laboratory investigations (where appropriate)
6. Summary of the safety and tolerance data, including details of all Adverse Drug Events (ADE) including any follow-up. Case histories of all serious ADEs or ADEs leading to withdrawal should be provided.
7. If appropriate, details of any statistical analysis carried out by the Investigators, and a summary of efficacy data including clinical observations.
8. Conclusions

A copy of the report will be forwarded to the Research Ethics Committee.

4.7 Curriculum Vitae

In accordance with international standards, and Good Clinical Research Practice, a signed copy of the curriculum vitae of the Principal Investigators, Research Physician/Co-Investigator, Statistician and members of the MEC study team will be provided to Thornton & Ross Ltd.

4.8 Case Record Form

The Investigator is required to prepare and maintain adequate and accurate case records that have been designed by Thornton & Ross Ltd to record all observations and other data pertinent to the clinical study. All CRFs should be completed in their entirety in a neat, legible manner to ensure accurate interpretation of data. Black ballpoint pen should be used to ensure the clarity of reproduced copies. Any alterations or errors to the CRF should be crossed through once only, and signed and dated by the person making the change, using black ballpoint pen.

The study monitor will examine the original CRFs at each monitoring visit and will approve them when the CRF is complete and any necessary amendments have been made. The Investigator will not sign the CRFs until the study monitor has approved them. The Investigator will retain the CRFs until completion of data collection when they will be given to the study monitor for transfer to Thornton & Ross Ltd. The Investigator will retain a copy together with other source data for his/her own files.

The CPMP Guidelines on Good Clinical Practice for Trials on Medicinal Products in the European Community require that the Investigator shall arrange for the retention of the participant identification codes for at least 25 years after the completion or discontinuation of the study. Participant files and other source data shall also be kept for the maximum period permitted by the institution but not less than 25 years.

